5.2 Per Protocol Set (PPS)

Not applicable to this study.

5.3 Safety Analysis Set (SAF)

For the statistical summary of the safety data, the safety analysis set (SAF) will be used. The SAF consists of all subjects who took at least one dose of study medication.

The SAF will be used for summaries of demographic and baseline characteristics and all safety and tolerability related variables.

5.4 Biomarker Analysis Set (BAS)

The Biomarker analysis set (BAS) consists of the subset of the FAS population for which biomarker data are available to facilitate derivation of at least one of the correlative biomarkers. The Total N used in summaries and analyses for each unique biomarker will be the number of subjects with data available for that unique biomarker.

6 ANALYSIS VARIABLES

The primary efficacy endpoint is:

- Radiographic progression-free survival (rPFS).

The secondary endpoints are:

- additional measures of efficacy:
 - Overall survival rate at 1 year
 - Time to PSA progression
 - PSA response rate [maximum decline of $\geq 30\%$, $\geq 50\%$, and $\geq 90\%$ from baseline, (PSA30, PSA50, and PSA90), respectively]
 - Objective response rate
- Time to first use of a subsequent antineoplastic therapy
- Safety of enzalutamide re-treatment in the post-chemo setting

Other efficacy endpoints:

- Composite PFS (cPFS), defined as the earliest date of either radiologic progression, clinical progression, or death

The exploratory endpoints are:

- Correlative science in the post-chemo setting.

6.1 Efficacy Endpoints

6.1.1 Primary Efficacy Endpoint(s)

The primary efficacy endpoint is radiographic progression-free survival (rPFS), which is defined as time from first dose to the radiological progression event or death.

The radiological PFS event is either radiological disease progression defined by either soft tissue tumor progression defined by RECIST 1.1, or the bone progression defined by the Prostate Cancer Clinical Trials Working Group 2 (PCWG2). The bone progression per PCWG2 is defined as a minimum of two new lesions are observed. Progression on bone scan at time points prior to or at Week 9 requires a confirmatory scan performed six or more weeks later. This confirmatory scan should demonstrate at least 2 additional new lesions (PCWG2) compared to the week 9 scan.

rPFS will be censored in the following scenarios:

- If patient has neither PD nor death, the PFS will be censored at last radiological tumor assessment date.
- If patient had PD or Death occurred more 24 weeks (168 days) after previous tumor radiological assessment. The PFS will be censored at last radiological tumor assessment date.
- If patient does not have post baseline tumor assessment, nor death within 24 weeks (168) after first dose, the PFS will be censored at Day 1.
- If patient took any new anti-cancer therapy before any PD event, the PFS will be censored at the last radiological tumor assessment date prior to the date of new anti-cancer therapy.

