5.3 Efficacy Assessment

5.3.1 CT/MRI and Bone Scan

Imaging including abdominopelvic CT/MRI, chest CT (if screening chest x-ray leads to diagnosis of thoracic metastasis), and Technicium-99m (Tc-99m) bone scintiography will be performed at the Screening Visit and assessed at Week 9, Week 17, Week 25 and at subsequent 12 week intervals. For subjects that discontinue for reasons other than radiographic progression or initiation of a new anti-neoplastic therapy, the imaging will be conducted every 12 weeks until progression, initiation of new anti-neoplastic therapy, loss to follow-up or death. Imaging performed prior to informed consent may be used as baseline so long as it is performed within the Screening period (days -28 to -1).

Scans should be scheduled in such a way that the scan results are available at the regularly scheduled visit.

The imaging method utilized for baseline scans must be utilized throughout the entire study.

Imaging may be performed at any time to confirm suspected progression of disease.

Radiographic evaluation of metastatic disease is determined separately for soft tissue and bone disease. Radiographic disease assessment for soft tissue disease is based on CT or MRI scan and is defined by RECIST 1.1. Radiographic disease assessment for bone lesions is based on bone scan and progression is considered when a minimum of two new lesions compared to baseline are observed.

Progression on bone scan at time points prior to or at Week 9 require a confirmatory scan performed six or more weeks later. This confirmatory scan should demonstrate at least 2 additional new lesions compared to the Week 9 scan (PCWG2).

Assessment will include tumor measurements for target lesions, non-target lesions, and assessment for any new lesions. An overall assessment will be characterized for that time point evaluation. At the end of study for that subject, the overall best response to the study regimen will be characterized.

Images (abdominopelvic [lung when applicable] CT/MRI and bone scan) should be read on site. Each site should ideally designate the same reader who will evaluate the images for any one subject for the duration of the study.

The same imaging method used for an individual patient at baseline should be used throughout the entire study for that patient.

PET scans should not be used to determine disease progression.

5.3.2 **PSA**

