- j The window for all radiological assessments is ± 7 days. At Weeks 9, 17, 25 and subsequent assessments prior to treatment discontinuation, all other procedures must be completed within the ± 3 day window. Bone progression at the first reassessment at Week 9 requires a confirmatory scan 6 or more weeks later.
- k Adverse events, serious or non-serious, will be collected from the time the patient signs the consent form until the Safety Follow-Up visit, regardless of initiation of another anti-neoplastic therapy prior to last dose of enzalutamide.
- l Long-term follow-up for radiographic progressions (until progression or initiation of new anti-neoplastic therapy), survival, and subsequent anticancer therapies should be performed every 12 weeks for a maximum of 3 years from first dose. The study will end when the last subject has been followed for 1 year from date of first dose.
- m Enzalutamide will be administered until the disease progression, including radiographic progression or unequivocal clinical progression. Per the Investigator's clinical judgment and with sponsor approval, patients may be allowed to continue enzalutamide until the next treatment is initiated. If another non-cytotoxic, non-investigational, antineoplastic agent is initiated after protocol-defined progression has been determined, enzalutamide may be continued per the Investigator's clinical judgment and with sponsor approval as long as the patient is tolerating enzalutamide and continues androgen deprivation therapy
- n Blood samples for CTC molecular profiling and serum samples will be collected at baseline, week 13, time of PSA progression, and time of radiographic progression.

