4 SAMPLE SIZE

Prior clinical trials data in the post-chemo setting have shown the following median rPFS for subject randomized to initial placebo, placebo+prednisone, or mitoxantrone+prednisone therapy:

- AFFIRM: Placebo = 2.9 months
- COU-301: Placebo + Prednisone = 3.6 months
- TROPIC: Mitoxantrone + Prednisone = 1.4 months

With a sample size of 40 subjects and an assumed median rPFS of 4 months for the therapy defined in this single-arm study, approximately 34 events are expected over a 12-month accrual and 12-month minimum follow-up. Further assuming uniform accrual, 10% loss to follow-up, and an exponential distribution for the rPFS event times, the expected lower bound of the 90% confidence interval for the median is approximately 2.5 months based upon simulations.

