7.11.3 Visit Windows

Not applicable.

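### Once scans are 12 weeks apart, the 168-day rPFS censoring limit has no allowance for the ±7-day scan window, so after one missed scan a few days of scheduling decide between event and censoring

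*SAP*

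**What the plan says.** The second censoring rule for the primary endpoint in SAP 6.1.1 reads "If patient had PD or Death occurred more 24 weeks (168 days) after previous tumor radiological assessment". In that case rPFS is censored at the last radiological assessment. I read the limit as strictly more than 168 days, so a gap of exactly 168 days still counts as an event. The third rule uses the same 24 weeks counted from first dose: "If patient does not have post baseline tumor assessment, nor death within 24 weeks (168) after first dose" leads to censoring at Day 1.

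Protocol 5.3.1 has imaging "assessed at Week 9, Week 17, Week 25 and at subsequent 12 week intervals". The on-treatment scans are therefore nominally on Days 57, 113 and 169, then every 84 days. For subjects who stop drug without radiographic progression or new therapy, "the imaging will be conducted every 12 weeks until progression, initiation of new anti-neoplastic therapy, loss to follow-up or death". Protocol 6.1 counts those 12 weeks from the last dose. The footnote to the SAP flow chart adds: "The window for all radiological assessments is ± 7 days".

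Nothing in the SAP adds this window to the 168 days, and SAP 7.11.3 marks visit windows as not applicable. The primary analysis (SAP 7.4.1) is the Kaplan-Meier median with a two-sided 90% confidence interval.

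**The concern.** Since 168 = 2 × 84, the limit appears meant to tolerate one missed 12-weekly scan and to censor after two. However, two scans that are each within window can be up to 14 days further apart, or closer together, than their nominal spacing. After one missed 12-weekly scan the cut-off therefore sits at the centre of the range of compliant gaps.

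Two subjects with the same history, both scanned within window, can then get opposite status on the primary endpoint. One has an event at the progression scan. The other is censored at the previous scan, about 24 weeks earlier. The trial has 40 subjects and about 34 expected events, so each reclassified progression removes about 3% of the events (1/34).

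**Working it through.** **Planning model.** SAP 4 gives "With a sample size of 40 subjects and an assumed median rPFS of 4 months", exponential event times, 12-month uniform accrual, 12-month minimum follow-up and 10% loss to follow-up.
- Hazard λ = ln 2 / 4 = 0.1733 per month.
- Event-free probability averaged over follow-up of 12 to 24 months = (2⁻³ − 2⁻⁶) / (12λ) = 0.1094 / 2.079 = 0.053.
- Events: 40 × 0.947 = 37.9, and × 0.90 = 34.1. The plan's figure of about 34 is reproduced.

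**Gap after one missed scan.** Each scan is up to 7 days early or late. The screening scan is on Day −28 to −1, with no Day 0.

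| Missed scan | Previous → next scan | Nominal gap (days) | Range (days) | Can exceed 168? |
|---|---|---|---|---|
| Week 9 | Screening → Week 17 | – | 106–147 | No |
| Week 17 | Week 9 → Week 25 | 112 | 98–126 | No |
| Week 25 | Week 17 → Week 37 | 140 | 126–154 | No |
| Week 37 or later | 12-weekly scans | 168 | 154–182 | Yes |

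**Chance of censoring in the last row.** The distribution of scan offsets is not in the documents. I assume independent offsets, uniform on the 15 days from −7 to +7, which gives 225 pairs. In 15 pairs the gap is exactly 168 days (6.7%, event). In (225 − 15)/2 = 105 pairs it is longer: 105/225 = 46.7% censored. With offsets of only ±3 days the share is 21/49 = 43%. With normal offsets (SD 3 days) it is 45%.

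**How many subjects reach this phase.** At a 4-month median (121.75 days), 2^(−168/121.75) = 0.384 are event-free at Week 25, about 15 of 40.

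**Effect per trial.** This comes from simulation of 40 subjects, 1,500 trials per row, comparing 168 with 182 days. The miss rates are assumptions. Progression is detected only at scheduled scans, and deaths are not modelled.

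| True median | Missed per scan | Subjects changing status | Trials with changed KM median | Mean KM median, 168 / 182 (days) |
|---|---|---|---|---|
| 4 months | 5% | 0.42 | 0.6% | 156.5 / 156.5 |
| 4 months | 10% | 0.84 | 3.4% | 159.7 / 159.5 |
| 4 months | 20% | 1.46 | 14% | 168.5 / 168.5 |
| 8.3 months | 10% | 0.90 | 11% | 305.0 / 303.3 |

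The 8.3 months is the enzalutamide rPFS median quoted from AFFIRM in Protocol 1.2.

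The counts include some subjects whose first post-baseline scan is Week 25, because the simulation places the baseline scan on Day 1. Their expected number at the 4-month median is 40 × p² × (1 − p) × 0.616 × 7/15, where p is the miss rate. That is 0.03, 0.10 and 0.37 at 5%, 10% and 20%. The 12-week phase alone therefore accounts for about 0.4, 0.7 and 1.1 subjects, and the shares of changed medians are upper figures for it.

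**Early entry to the 12-week schedule.** Suppose a subject stops drug at about the Week 9 visit, without progression on the scan and without new therapy, and misses the first follow-up scan. The second follow-up scan is nominally 168 days after Day 57. If censored, this subject is censored at about Day 57, before the planned median at about Day 122.

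**Check of 182 days (168 + 7 + 7).**
- One missed 12-weekly scan: censored 0% instead of 46.7%.
- Two missed 12-weekly scans (gap 238–266 days): still always censored.
- Weeks 9 and 17 both missed: the gap from screening to Week 25 is 162–203 days. Of 28 × 15 = 420 equally likely date pairs, 392 (93%) exceed 168 days but only 210 (50%) exceed 182.

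**The case against.** The strongest reply is that any day limit has an edge and that this one hardly touches the reported result. Under the planning model most progressions occur before the 12-week phase. The average median moves by less than one day at 4 months, and by about two days at 8.3 months. This stands, and it is why the point is minor.

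Three further objections stand in part.
- The size rests on miss rates and scan offsets that the documents do not give. Protocol 5.3.1 also allows imaging at any time for suspected progression. That would shorten some gaps, so the counts are probably on the high side.
- The ambiguity concerns progression found at a scan. Deaths fall under the same rule but are not tied to scan dates, so they do not cluster at the limit.
- Replacing 168 by 182 throughout is not free. It would split subjects who miss both Week 9 and Week 17 about evenly, where the present rule treats 93% of them alike. This assumes that the screening scan counts as the previous assessment.

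A reader might infer that any missed scan leaves the outcome to chance. The schedule does not support that: the gap after one missed Week 9, 17 or 25 scan is at most 154 days, so progression at the next scan within window is always an event.

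What the reply does not remove is that this edge lies at the centre of the compliant range for the very case it seems meant to tolerate.

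**Conclusion.** The point holds for the 12-week imaging phase, on or off treatment. There, after one missed scan and a next scan within window, event or censoring is close to a coin toss: about 47% censored with uniform offsets, 43% to 45% with tighter ones. With assumed miss rates of 5% to 20%, about 0.4 to 1.5 of 40 subjects change status.

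It would be tempting to conclude that the primary median is unreliable, or that every exposed subject loses a progression. Neither follows. The median changes in about 1% to 15% of simulated trials at 4 months, and in about 11% at 8.3 months with 10% missed. Slightly more than half of the exposed subjects keep their event. On the on-treatment schedule the affected subjects are censored no earlier than about Day 162. The effect should therefore fall mainly on the later curve and the upper confidence limit; that last step is reasoning, as the limit itself was not simulated. This is an inexpensive improvement, not a flaw that threatens the analysis.

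**What to change.** Amend the second censoring rule in SAP 6.1.1 before database lock (SAP 1 allows revisions until hard lock), in one of two ways.

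1. Preferred: censor progression or death at the last scan only after two or more consecutive scheduled scans have been missed, a scan being missed once its ±7-day window has passed. This also covers off-treatment subjects whose last dose, and hence 12-week clock, falls well after their last scan.
2. If a day count is kept: more than 182 days where the scans concerned are on the 12-week schedule, and 168 days for the earlier 8-week phase.

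In either case, state how the 24-week limit in the third rule relates to the revised rule, and whether the screening scan counts as a previous assessment.

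The cost is slightly more programming, and a few progressions accepted up to two weeks later than now. Option 1 also bites earlier in the 8-week phase. After a Week 9 scan on Day 57, the Week 25 window closes on Day 176, 119 days later. A death, or progression on an unscheduled scan, between then and day 168 of the gap would move from event to censored. If that is not wanted, require both conditions (two missed scans and more than 168 days) or use option 2.

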Subjects that discontinue study drug for a reason other than radiographic progression or initiation of a new anti-neoplastic therapy will have a PSA test performed 30 days from date of last dose and undergo long-term follow-up every 12 weeks from date of last dose. Long term follow-up will assess for survival, subsequent anti-neoplastic therapy for prostate cancer and radiographic progression. Subjects will be followed for a maximum of 3 years from first dose. The study will end when the last subject has been followed for 1 year from date of first dose. Radiographic imaging will end when the patient has developed a radiographic progression, or initiated subsequent anti-neoplastic therapy. Reasonable effort should be made to contact any subject lost to follow-up during the course of the study in order to complete study related assessments and retrieve any outstanding data and study drug. Following unsuccessful telephone contact, an effort to contact the subject by mail using a method that provides proof of receipt should be attempted. Such efforts should be documented in the source documents.

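### The missed-scan rule for rPFS does not anchor its censoring date before the progression; read literally, it censors a progression found after a long gap at the progression scan itself

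*SAP*

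**What the plan says.** SAP 6.1.1 lists four censoring scenarios for rPFS. Three matter here.

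- **First scenario (neither PD nor death):** "the PFS will be censored at last radiological tumor assessment date". Here the phrase can only mean the final scan on file.
- **Second scenario (missed scans):** the condition is "If patient had PD or Death occurred more 24 weeks (168 days) after previous tumor radiological assessment". The consequence repeats the first scenario's phrase, with no qualifier.
- **Fourth scenario (new therapy before PD):** "the PFS will be censored at the last radiological tumor assessment date prior to the date of new anti-cancer therapy". This date is anchored before the intervening event.

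Imaging "will be performed at the Screening Visit and assessed at Week 9, Week 17, Week 25 and at subsequent 12 week intervals" (Protocol 5.3.1). The timing allowance is given in the SAP flow chart: "The window for all radiological assessments is ± 7 days". On when scans stop, Protocol 6.1 says: "Radiographic imaging will end when the patient has developed a radiographic progression, or initiated subsequent anti-neoplastic therapy".

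Nothing else in the protocol or SAP defines 'last' for the missed-scan rule. SAP 7.11 refers to a separate data specification for details, which is not among the documents.

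**The concern.** The rule measures the gap from one scan ('previous') and names another ('last') as the censoring date. For a death the two are the same scan. For a progression they need not be: the scan that ends the gap is the scan that shows the PD, and imaging then stops, so it is normally the last one on file.

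A missed-scan rule usually stops follow-up where observation became unreliable. The literal wording instead credits the whole unobserved interval and also discards the event that ended it. That is more favourable than counting the PD as an event on that date, and more favourable than censoring at the scan before the gap. The endpoint affected is the primary one. Both readings censor the subject, so the reported number of events would not show which had been programmed.

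**Working it through.** **1. The plan's own figures.** The SAP states: "With a sample size of 40 subjects and an assumed median rPFS of 4 months for the therapy", and "approximately 34 events are expected over a 12-month accrual and 12-month minimum follow-up". Its other inputs are uniform accrual, exponential event times and 10% loss to follow-up.

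- λ = ln 2 / 4 = 0.1733 per month.
- P(event) = 1 − (e^(−12λ) − e^(−24λ)) / (12λ) = 1 − (0.1250 − 0.0156) / 2.079 = 0.947.
- 40 × 0.947 = 37.9, and × 0.9 for loss = 34.1. This matches 34.
- Simulated lower 90% limit for the median (2,000 runs, Brookmeyer-Crowley, log-log): 2.54 months with n = 36, and 2.66 to 2.68 with n = 40 and 10% random loss. The plan says about 2.5.

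As reproduced, these figures use no scan schedule and no missed-scan rule, so the wording does not touch them.

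**2. One subject.** Scans at Week 9 (Day 57) and next at Week 37 (Day 253), with PD on the second.

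- Gap: 253 − 57 = 196 days, above 168, so the rule applies.
- 'Last' = PD scan: censored at 253 / 30.44 = 8.3 months.
- 'Last' = previous scan: censored at 57 / 30.44 = 1.9 months.

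**3. Direction.** Both readings have the same events at the same times. The PD-scan reading keeps the gap subject in the risk set longer. Each factor 1 − d/n is therefore equal or larger, and the curve is never lower on the same data.

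**4. Size.** The simulated trials have 40 subjects, a true median of 4 months and the plan's scan schedule. The share of subjects missing scans is an assumption. Entries are mean Kaplan-Meier medians in months.

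| Scans missed | Share | Previous-scan reading | PD-scan reading | Difference |
|---|---|---|---|---|
| Weeks 17 and 25 (1,500 trials) | 5% | 5.06 | 5.04 | −0.02 |
| | 10% | 5.14 | 5.26 | +0.12 |
| | 20% | 5.26 | 5.79 | +0.53 |
| Two in a row, starting at Week 9, 17 or 25 at random (800 trials) | 5% | 5.03 | 5.04 | +0.01 |
| | 10% | 5.10 | 5.18 | +0.08 |
| | 20% | 5.25 | 5.54 | +0.29 |
| Three in a row, same starts (800 trials) | 5% | 5.02 | 5.08 | +0.06 |
| | 10% | 5.13 | 5.38 | +0.25 |
| | 20% | 5.11 | 5.78 | +0.67 |

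- The medians exceed 4 because PD is dated at the scan that finds it.
- By step 3 the difference cannot be negative on the same data, so −0.02 should be read as zero.
- With two in a row missed, the rule catches on average 0.7, 1.5 and 3.1 progressions per 40 subjects. With three, it catches 1.1, 2.3 and 4.5.
- The lower 90% limit differs by 0.02 to 0.36 months across the two 800-trial settings.
- Counting these PDs as events at the PD scan gives 5.02, 5.13 and 5.39 for two in a row. At 20% that lies between the two readings (5.25 and 5.54).

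**5. How easily the rule is triggered.** After Week 25, scans are 84 days apart, so one missed scan leaves a gap of 168 ± 14 days. If each visit falls uniformly on one of 15 days (assumption), 15 of the 225 pairs give exactly 168 days and half of the other 210 exceed it: 105 / 225 = 47%. These gaps mostly come after the median and affect the later part of the curve.

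**The case against.** The strongest reply is that the rule is one sentence broken by a stray full stop. The scan it has just named is the 'previous' one, and 'last' can naturally refer back to it. The phrase must also serve deaths, where the last scan is the previous scan. This is a fair reading and may be the intended one. It does not settle the text, because the first scenario uses the same phrase for the final scan on file and the fourth scenario adds the anchor that is missing here.

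A second reply is that any analysis dating PD at the detecting scan keeps the subject at risk through the gap, and that nobody knew during the gap that he had progressed. That is correct. Time at risk alone is therefore not the fault. The fault on the literal reading is to credit that time and also drop the event observed at its end.

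Third, the effect is near zero unless long gaps are common, and the documents give no missed-scan rate. The study is single-arm and descriptive: it reports a median with a 90% interval and sets no decision threshold. This also stands, and it keeps the point minor.

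Finally, the data specification cited in SAP 7.11 may already define the date. That cannot be checked here, and a primary-endpoint rule should be clear in the SAP itself.

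**Conclusion.** The rule is wrong as written on its literal reading, and the other available reading is sound. The severity is low: a clarification worth making.

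Relative to censoring at the previous scan, the literal reading raises the median rPFS by about 0 months if 5% of subjects miss two consecutive scans, about 0.1 if 10% do, and 0.3 to 0.5 if 20% do. The spread at 20% depends on which two scans are missed. If three in a row are missed, the shift reaches about 0.7 months at 20%. All these rates are assumptions.

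A reader might infer that the SAP definitely censors at the progression scan, that the primary estimate will be materially inflated, or that the sample size is undermined. The documents support none of these. The wording allows two readings, the larger shifts need one subject in five to miss consecutive scans, and the 34 events and 2.5-month lower limit do not depend on the rule. Deaths after a gap are censored at the same scan on either reading.

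**What to change.** In SAP 6.1.1, replace the second sentence of the missed-scan scenario with:

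*rPFS will be censored at the last radiological tumor assessment before the PD or death (Day 1 if no post-baseline assessment precedes it).*

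The anchor should be the PD or death, not the gap: a subject may have had an earlier long gap that ended in a scan without progression. The Day 1 clause covers a subject whose first post-baseline scan shows PD more than 168 days after the screening scan. The no-post-baseline-assessment scenario does not reach him, because he has such a scan.

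Check that the data specification uses the same date. If wanted, add a sensitivity analysis that counts these progressions and deaths as events on the date observed; it would show how much the rule matters in the actual data.

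The cost is one phrase. No new data and no sample-size change are needed, and SAP section 1 allows revisions before database hard lock.
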